5.2. Study Drug

Detailed information describing the preparation, administration, and storage of study drug (patisiran and placebo) is provided in the Pharmacy Manual.

All patients will be instructed to take the recommended daily allowance of vitamin A while on the study.

5.2.1. Premedication

All patients will receive premedication prior to study drug administration to reduce the risk of IRRs. Each of the following medicinal products should be given on the day of study drug infusion at least 60 minutes prior to the start of infusion:

- Intravenous corticosteroid (dexamethasone 10 mg or equivalent)
- Oral paracetamol (500 mg)
- Intravenous H1 blocker (diphenhydramine 50 mg, or equivalent; IV or oral nonsedating H1 blockers are acceptable.)
- Intravenous H2 blocker (ranitidine 50 mg, or equivalent)

Oral premedication equivalents are permitted, but must be administered in the presence of a healthcare professional.

Modifications to lower the corticosteroid dose may be made to the premedication regimen for either of the following 2 reasons:

1. Double-blind and open-label periods: If a patient is having difficulty tolerating the steroid premedication regimen (eg, patient develops uncontrolled hyperglycemia, altered mental status, or other complication), then lowering of the steroid premedication may be allowed for that patient after consultation with the medical monitor at any time during the study.
2. Double-blind period: For patients who are tolerating their double-blind study drug infusions well with their current corticosteroid premedication regimen (ie, no IRRs during the past 3 or more infusions), corticosteroid dose may be reduced in 2.5 mg increments to a minimum dose of 5 mg of dexamethasone (IV) or equivalent.
 - a. Open-label period: At the start of the open-label period, patients must take dexamethasone 10 mg or the equivalent as their corticosteroid premedication. Patients taking more than 10 mg of dexamethasone at the end of the double-blind period should take the higher dose. The corticosteroid dose may then be tapered as described above if the patient is tolerating infusions. However, if a patient's steroid premedication had been decreased in the double-blind period due to their inability to tolerate the premedication regimen as described above, continuation of the reduced dose regimen (as it had been in the double-blind period) may be permitted after consultation with the Medical Monitor.

Infusions during corticosteroid tapering may be performed at the study center or at a location other than the study center (eg, at home), as described in detail in the Pharmacy Manual, at the discretion of the Investigator and after consultation with the Medical Monitor.

Additional or higher doses of 1 or more of the premedications may be administered to reduce the risk of IRRs, if needed. For suggested guidelines for management of IRRs, see Section 5.2.4; further details can be found in the Pharmacy Manual.

5.2.2. Study Drug Description

Patisiran is a RNAi therapeutic consisting of a double-stranded siRNA targeting TTR mRNA formulated in an LNP. The patisiran drug product is a sterile formulation of ALN-18328 (siRNA targeting TTR) formulated as LNPs with lipid excipients (1,2-Dilinoleyoxy-N,N-dimethylpropylamine [DLin-MC3-DMA], 1,2-Distearoyl-sn-glycero-3-phosphocholine (DSPC), cholesterol, and PEG₂₀₀₀-C-DMG) in isotonic phosphate buffered saline. Patisiran Solution for IV infusion contains 2 mg/mL of patisiran.

See the Pharmacy Manual for further details of solution concentration and fill volume.

The control drug for this study will be a placebo (normal saline 0.9% for IV administration). Control drug will be provided by a central supplier (or, if necessary, by a local supplier, with prior Sponsor approval).

5.2.3. Dose and Administration

Detailed instructions for study drug preparation and administration are found in the Pharmacy Manual.

5.2.3.1. Double-blind Study Drug (Patisiran or Placebo)

All patients will receive premedications prior to study drug administration to reduce the risk of IRRs (Section 5.2.1).

An IV infusion of double-blind study drug (patisiran 0.3 mg/kg or placebo) will be administered under the supervision of the site personnel once every 3 weeks \pm 3 days.

The amount (in mg) of double-blind patisiran to be administered should be determined based on the patient's weight (kg). Dosing is based on actual body weight. For patients weighing \geq 100 kg, the maximum recommended dose is 30 mg.

Weight from the previous visit may be used for calculating dose. Weight must be collected prior to dosing with study drug. Study drug will be administered as an approximately 80-minute IV infusion (approximately 1 mL/minute for the first 15-minutes followed by approximately 3 mL/minute for the remainder of the infusion). The patient's infusion site should be assessed for signs of any localized reaction during the infusion and for 30 minutes after the end of the infusion. The patient will be observed for 1 hour following completion of dosing for observation and completion of assessments.

Patients who have received \geq 2 doses of study drug at the study center with no evidence of IRRs or other drug-related adverse effects that impact safety and tolerability of the infusion may have study drug administered at a location other than the study center (eg, at home), where applicable country and local regulations allow. Study drug administration will be performed by a healthcare professional, trained on the protocol and on administration of premedications and study drug infusion, with oversight of the Investigator.

Missed doses of double-blind study drug

If a patient does not receive a dose of study drug within the dosing window (\pm 3 days), the delayed dose may be taken up to 7 days after the scheduled visit (ie, +4 days after the +3-day dosing window per the Schedule of Assessments [Table 1]), after consultation with the Medical

Monitor. If a dose is administered with a delay, the next dose will resume following the original schedule per the Schedule of Assessments.

A dose will be considered completed if 80% or more of the total volume of the IV solution has been administered to the patient. Patients will be permitted to miss an occasional dose of study drug. However, if a patient misses 2 consecutive doses for reasons unrelated to the COVID-19 pandemic, the Investigator, in consultation with the Medical Monitor, will discuss whether the patient will be able to continue in the study.

5.2.3.2. Open-label Extension Period (Patisiran)

The last dose of double-blind study drug will be at Week 51 and the first dose of open-label patisiran will be 3 weeks later (at Week 54) and thereafter every 3 weeks (± 3 days) for the remainder of the study. Open-label patisiran will be administered per the schedule and dose as is described in Section 5.2.3.1 for double-blind patisiran. As noted in Section 3.6, blinding will be maintained until the last patient completes their Month 12 visit.

During the open-label extension period, patients who have received at least 2 doses of open-label patisiran at the study center with no evidence of IRRs or other drug-related adverse effects that impact safety and tolerability of the infusion may have patisiran administered at a location other than the study center (eg, at home), where applicable country and local regulations allow. Patisiran administration will be performed by a healthcare professional trained on the protocol and administration of premedications and patisiran infusion.

All patients will receive premedications prior to open-label patisiran administration to reduce the risk of IRRs (Section 5.2.1).

Missed doses of open-label patisiran

If a patient does not receive a dose of open-label patisiran within the dosing window (± 3 days), the delayed dose may be taken up to 7 days after the scheduled visit (ie, +4 days after the +3-day dosing window per the Schedule of Assessments [Table 2, Table 3, and Table 4]), after consultation with the Medical Monitor. If a dose is administered with a delay, the next dose will resume following the original schedule per the Schedule of Assessments.

5.2.4. Suggested Guidelines for Management of Infusion-related Reactions

Criteria for categorizing IRRs are provided in Section 10.3.

- In the event of an IRR, the infusion of study drug may be slowed or stopped and the patient closely monitored until resolution of the reaction. Drugs that may be used to facilitate resolution and permit resumption of study drug administration include but are not limited to: paracetamol/acetaminophen (or equivalent), additional histamine H1/H2 receptor antagonists (eg, ranitidine), nonsteroidal anti-inflammatory drugs (NSAIDs), adrenaline, supplemental oxygen, IV fluids, and/or corticosteroids.
- Following resolution of a mild or moderate IRR that required interruption of the study drug infusion, resumption of administration may occur at the Investigator's discretion at a slower infusion rate for that dose and for subsequent doses of study drug. If the infusion is delayed, the administration of the infusion should be completed no more than 16 hours after study drug is first diluted in saline (including infusion time).

- Study drug administration will not be resumed for any patient following a severe IRR until the case is discussed with the Medical Monitor.
- If after consultation with the Medical Monitor it is agreed that an individual patient's steroid premedication will be increased, then the following steps are **recommended**:
 1. If the IRR occurred while the patient received 10 mg IV dexamethasone or equivalent at least 60 minutes before the infusion and did not resolve with slowing of the infusion rate, then the patient should be increased by multiples of 5 mg IV dexamethasone or equivalent at least 60 minutes before the infusion.
 2. Increased dose of premedication steroids should NOT exceed the combination of 20 mg IV dexamethasone or equivalent on the day of infusion.
 3. If the IRR occurred while the patient received less than 10 mg IV dexamethasone or equivalent, then the patient should return to the prior dose of IV dexamethasone or equivalent that did not result in an IRR.

Patients will be instructed to call the Investigator if they experience symptoms such as fever, chills, myalgia, or nausea/vomiting after discharge from the site.

5.2.5. Dose Modifications

Dose modifications are not permitted.

If a study drug-related AE occurs in a patient that the Investigator judges as presenting a potential risk to the patient for further dosing, the study drug dose may be held at the discretion of the Investigator and the Medical Monitor should be contacted.

5.2.6. Preparation, Handling, and Storage

Staff at each clinical study center or the home healthcare professional will be responsible for preparation of study drug (patisiran and placebo) doses, according to procedures detailed in the Pharmacy Manual. No special procedures for the safe handling of study drug are required.

Study drug will be stored upright and refrigerated at approximately (5 ±3°C) until dose preparation. Deviations from the recommended storage conditions should be reported to the Sponsor and use of the study drug halted until authorization for its continued use has been provided by the Sponsor or designee, as described in the Pharmacy Manual.

A Sponsor representative or designee will be permitted, upon request, to audit the supplies, storage, dispensing procedures, and records.

Instructions specific to unused study drug and additional storage will be provided in the Pharmacy Manual.

5.2.7. Packaging and Labeling

All packaging, labeling, and production of study drug will be in compliance with current Good Manufacturing Practice specifications, as well as applicable local regulations. Study drug labels and external packaging will include all appropriate information as per local labeling requirements. Additional details will be available in the Pharmacy Manual.

5.2.8. Accountability

The Investigator or designee will maintain accurate records of receipt and the condition of the study drug supplied for this study, including dates of receipt. In addition, accurate records will be kept of when and how much study drug is dispensed and administered to each patient in the study. Any reasons for departure from the protocol dispensing regimen must also be recorded.

At the completion of the study, there will be a final reconciliation of all study drugs. Used, partially used, and unused study drug will be returned to the Sponsor (or designee) or destroyed at the clinical study center according to applicable regulations.

Further instructions about drug accountability will be detailed in the Pharmacy Manual.

5.3. Concomitant Medications and Procedures

All patients will receive premedications prior to study drug administration to reduce the risk of IRRs (Section 5.2.1).

Use of the following medications/treatments are prohibited during study participation:

- Any investigational agent other than study drug.
- Inotersen, doxycycline, ursodeoxycholic acid, taurooursodeoxycholic acid, and diflunisal are also prohibited during the study (see exclusion Criterion 10 in Section 4.2). Doxycycline is permitted if being taken for short-term treatment of infection.

All patients will be asked to take the recommended daily allowance of vitamin A for the duration of their participation in the study while being administered study drug. In countries where relevant, the clinical sites will provide patients with a prescription for vitamin A at a dose consistent with local guidelines.

Standard vitamins and topical medications are permitted. Any concomitant medication or treatment that is required for the patient's welfare may be given by the Investigator. However, it is the responsibility of the Investigator to ensure that details regarding the medication are recorded on the CRF, as specified in the Schedule of Assessments (Table 1, Table 2, Table 3, and Table 4). Concomitant medications include all prescription medications, herbal preparations, over the counter medications, vitamins, and minerals. Any changes in medications during the study will also be recorded on the CRF. Concomitant medication will be coded using an internationally recognized and accepted coding dictionary.

5.3.1. Concomitant Tafamidis Use

Per inclusion Criterion 4, at baseline patients are either: 1) tafamidis naïve or 2) currently on tafamidis for ≥ 6 months with demonstrated disease progression, as determined by the Investigator. Patients who have been on tafamidis for ≤ 30 days total and have not received any tafamidis in the 6 months prior to baseline will be considered tafamidis naïve and may qualify for the study.

For patients on tafamidis at baseline, the reasons for considering the patient to have demonstrated disease progression will be recorded in the eCRF. Patients who are on tafamidis at

baseline are encouraged, if it is medically appropriate in the opinion of the Investigator, to remain on tafamidis for the duration of the double-blind period.

Per exclusion Criterion 8, patients who are tafamidis naïve at baseline, for whom the Investigator actively plans or anticipates commencing treatment with tafamidis during the 12-month double-blind period (taking into consideration clinical status, patient preference, and/or commercial availability of tafamidis), should not be enrolled in the trial.

However, if tafamidis is granted approval by a Health Agency for treatment in patients with ATTR amyloidosis with cardiomyopathy in a given region, all enrolled patients in this region will be made aware of its potential benefits and risks at the time of regulatory approval and all patients will be reconsented. In such circumstances, tafamidis is not considered prohibited and the Investigator may, using their medical judgement, commence concomitant on-label tafamidis during the study, if it is felt to be in the best interest of the patient and if it is commercially available in the country.

Patients who are tafamidis naïve at baseline, but begin taking commercial tafamidis (ie, “tafamidis drop-in”), will remain in the study. Prior to commencing concomitant tafamidis, the Investigator will perform assessments (including primary and select secondary efficacy assessments) at the Pre-tafamidis Drop-in Visit, as outlined in the Schedule of Assessments ([Table 1](#)). In all cases, the Pre tafamidis Drop-in Visit should occur prior to starting concomitant tafamidis; where possible, this visit should occur between 1-2 weeks after the last dose of study drug (ie, 7 to 14 days post study drug dose). Thereafter, the patient will continue with all assessments per the Schedule of Assessments ([Table 1](#), [Table 2](#), [Table 3](#), and [Table 4](#)). In addition, at the time of tafamidis drop-in, the reason for starting tafamidis will be recorded in the CRF.

Initiation of TTR stabilizer therapies other than tafamidis (eg, diflunisal) is not allowed during the double-blind period of this study.

5.4. Treatment Compliance

Compliance with study drug administration will be verified through observation by study staff or trained home healthcare professionals.

5.5. Other Requirements

5.5.1. Contraception

Females of child-bearing potential must be willing to use a highly effective method of contraception from 14 days before first dose, throughout study participation, and for 12 weeks after the last dose of study drug in this study.

Birth control methods which are considered highly effective include:

- Placement of an intrauterine device.
- Placement of an intrauterine hormone-releasing system.
- Bilateral tubal occlusion.

- Surgical sterilization of male partner (with the appropriate post-vasectomy documentation of the absence of sperm in the ejaculate; for female patients on the study, the vasectomized male partner should be the sole partner for that patient).
- Established use of oral (except low-dose gestagens), implantable, injectable, or transdermal hormonal methods of contraception.
- True sexual abstinence, when in line with the preferred and usual lifestyle of the patient. Periodic abstinence (eg, calendar, ovulation, symptothermal, post-ovulation methods) and withdrawal are not acceptable methods of contraception. Abstinent patients must agree to use one of the above-mentioned contraceptive methods if they start heterosexual relationships during the study and for up to 12 weeks after the last dose of study drug.

Investigators should advise females of childbearing potential of the most appropriate birth control method available within their country taking into account local medical practice.

Females of child-bearing potential include female patients who have experienced menarche (or begin menarche over the course of the study), and who are not postmenopausal or permanently sterilized (eg, bilateral tubal occlusion, hysterectomy, or bilateral salpingectomy). A postmenopausal state is defined as the absence of menses for 12 months without an alternative medical cause, confirmed by follicle stimulating hormone level within the postmenopausal range.

For male patients, no contraception is required. However, use by males of contraception (condom) may be required in some countries, eg, France, in order to comply with local requirements as described in the corresponding patient informed consent forms.

Compliance with contraception requirements will be assessed on a regular basis by the Investigator throughout the course of the study (see Section [6.5.5.2](#)).

6. STUDY ASSESSMENTS

The Schedule of Assessments is provided in [Table 1](#) (double-blind period) and [Table 2](#), [Table 3](#), and [Table 4](#) (open-label extension period). Additional information on the collection of study assessments will be detailed in the respective reference manuals.

6.1. Screening Assessments

An ICF that has been approved by the appropriate Institutional Review Board (IRB)/Independent Ethics Committee (IEC) must be signed by the patient or legal guardian before the Screening procedures are initiated. All patients or their legal guardians will be given a copy of the signed and dated ICF. In addition, a medical records release form will be required of all patients for the purpose of obtaining vital status information from the patient's physician or from death registries.

See the Schedule of Assessments ([Table 1](#)) for a list of Screening visit assessments.

To ensure patient safety and, to the extent possible, that study integrity is maintained amid travel and other restrictions related to the COVID-19 pandemic, the Investigator will notify the Sponsor

before screening patients to allow an assessment of the ability of the study center or any new trial participant to comply with the protocol given COVID-19 limitations.

Patients will be screened to ensure that they meet all the inclusion criteria and none of the exclusion criteria. Rescreening (once) of patients is permitted with consultation of the Medical Monitor (see Section 6.1.2).

Patient demographic data and medical history/disease history will be obtained, including completion of ophthalmologic history in the eCRF. Any changes to medical history occurring between the screening assessment and Day 1 will be updated prior to study drug administration.

If a genetic test result that shows the presence or absence of a TTR pathogenic mutation, which would be consistent with either wtATTR or hATTR, is not available at Screening for the assessment of eligibility (Section 4.1, inclusion Criterion 2a), genotyping may be conducted at a central laboratory. Alternatively, a local laboratory may be selected by the study center in consultation with the Medical Monitor.

The study eligibility biopsies and technetium scintigraphy noted in inclusion Criterion 2 are intended to be historical, as part of the patient's clinical care and diagnosis, and are not performed as part of the study.

If a diagnostic result that confirms ATTR amyloidosis is not available at Screening for the assessment of eligibility (inclusion Criterion 2c/d), testing may be conducted at a laboratory or diagnostic center selected by the study center, in consultation with the Medical Monitor, in countries in which this test is not standard of care.

An echocardiogram will be performed at screening Visit 1 and results confirmed centrally to assess study eligibility, as indicated in the Schedule of Assessments (Table 1).

6.1.1. Retesting

If in the Investigator's judgement, the screening laboratory abnormalities are likely to be transient, then laboratory tests, may be repeated. The Investigator's rationale should be documented. Laboratory values can be retested once during screening provided that the patient can be evaluated for eligibility and randomized within the allowed Screening period. Any additional repeat testing may be considered after discussion with the Medical Monitor.

6.1.2. Rescreening

A patient who does not meet all study eligibility criteria due to a transient condition observed at screening, or who fails to complete screening activities due to unforeseen or unavoidable circumstances, may be rescreened once after consultation with the Medical Monitor after a minimum of 5 days have elapsed from a patient's last screening assessment. A patient will be re-consented if rescreening occurs outside of the 45-day screening window. In this case, all screening procedures must be repeated.

Patients who failed screening due to situations related to the COVID-19 pandemic may be allowed to rescreen after consultation with the Medical Monitor.

6.2. Efficacy Assessments

As noted in [Table 1](#), in situations where a Month 6 (Day 176-183), Month 9 (Day 260-267), and/or Month 12 (Day 365-372) study visit is unable to be completed at the study center due to the COVID-19 pandemic impacting activities at the study center or patient ability or willingness to access the study center or their ability to receive their scheduled doses of study drug, the Medical Monitor should be consulted as soon as possible to determine the appropriate timing of the Month 6, 9, and/or 12 efficacy assessments. After consultation with the Medical Monitor, efficacy assessments may be extended as follows: Month 6 up to Day 214; Month 9 up to Day 319; Month 12, up to Day 417, but prior to the first dose of open-label patisiran. Patients may continue to receive double-blind study drug until the Month 12 efficacy assessment is performed.

For the open-label extension period, as noted in [Table 2](#), in situations where a Month 18 (Day 554-561), Month 21 (Day 638-645), and/or Month 24 (Day 743-750) study visit is unable to be completed at the study center due to the COVID-19 pandemic impacting activities at the study center or patient ability or willingness to access the study center or their ability to receive their scheduled doses of study drug, the Medical Monitor should be consulted as soon as possible to determine the appropriate timing of the Month 18, 21, and/or 24 efficacy assessments. After consultation with the Medical Monitor, efficacy assessments may be extended as follows: Month 18 up to Day 592; Month 21 up to Day 697; Month 24, up to Day 791.

Similarly, for Years 3 and 4, in situations where a study visit at which efficacy assessments were to be performed is unable to be completed at the study center, the Medical Monitor should be consulted as soon as possible to determine the appropriate timing of the efficacy assessments for those visits. After consultation with the Medical Monitor, efficacy assessments may be extended, as described in [Table 3](#) and [Table 4](#).

6.2.1. 6-Minute Walk Test (6-MWT)

The 6-MWT, which will be assessed as the primary endpoint, is an assessment of functional exercise capacity. The 6-MWT will be administered by staff trained in the procedure per the relevant study manual. The staff administering the 6-MWT will be different from the Investigator or designee managing the care of the patient.

The 6-MWT will be performed at each of the timepoints specified in the Schedule of Assessments ([Table 1](#), [Table 2](#), [Table 3](#), and [Table 4](#)). At screening Visit 1, the 6-MWT will be administered for study eligibility purposes (per inclusion Criterion 6 [Section 4.1]). At screening Visit 1, prior to conducting the 6-MWT, the site staff will familiarize the patient with the purpose and conduct of the 6-MWT, as described in detail in the relevant study manual. Familiarization can be repeated at other timepoints if deemed helpful.

On Day 1 (baseline), which is a dosing day, the 6-MWT will be performed prior to study drug administration. (No other dosing days have a 6-MWT assessment.)

Patients who are hospitalized during the study should wait at least 2 weeks after hospitalization before completing a 6-MWT assessment; less time post-hospitalization may be permitted if, in the opinion of the Investigator, the patient is unencumbered due to the recent hospitalization. In addition, if a patient is not feeling well due to an external factor (eg, flu, sprained ankle, pulled

back muscle) at a visit when the 6-MWT will be performed, the test should not be done and should be rescheduled for another day within the permitted visit window.

For each 6-MWT assessment, the site should make every effort to have this assessment performed by the same assessor and to perform the test at approximately the same time of day. If the test is interrupted or deemed unusable by the 6-MWT core laboratory, the 6-MWT should be repeated as soon as possible within the allowed visit window.

Further details regarding the 6-MWT are provided in the relevant study manual.

A 1.5-month window will be used to group 6-MWT assessments to the Month 6 (Weeks 25-26), Month 9 (Weeks 37-38), and Month 12 (Weeks 52-53) visits. During the double-blind period, a patient may opt to begin tafamidis treatment or to discontinue study treatment, in which case they would complete a Pre-tafamidis Drop-in Visit ([Table 1](#)) or Early Treatment Discontinuation Visit ([Table 4](#)), respectively. To avoid the potential training effect from repeated assessments of the 6-MWT within a short period of time, only one 6-MWT assessment should be collected for the following time periods: Day 2 to Day 214 (for Month 6), Day 215 to Day 319 (for Month 9), and Day 320 to Day 417 (for Month 12).

Within a given time period, the 6-MWT assessment should be performed at whichever visit occurs first (scheduled assessment, Pre-tafamidis Drop-in Visit, or Early Treatment Discontinuation Visit); no additional 6-MWT assessments should be made in that time period. In later time periods, the 6-MWT should be assessed per the Schedule of Assessments ([Table 1](#)).

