1.3.1.1. Cardiac Results and Cardiac Subpopulation Data from APOLLO

In APOLLO, evidence of potential cardiac amyloid involvement was seen in most patients in the study; 80% had left ventricular wall thickness >13 mm and 79% had abnormal levels of the cardiac biomarker N-terminal prohormone B-type natriuretic peptide (NT-proBNP).[\[Solomon 2018\]](#) As well, 56% of the population met the prespecified criteria for inclusion in a subpopulation of patients with evidence of cardiac amyloid involvement (ie, the cardiac subpopulation, with baseline left ventricular wall thickness \geq 13 mm and no history of hypertension or aortic valve disease). In these patients, treatment with patisiran for up to 18 months resulted in improvement relative to placebo in important measures of cardiac structure and function. These included reduction in ventricular wall thickness and decrease (improvement) in global longitudinal strain.[\[Solomon 2018\]](#) In addition, patisiran treatment led to a reduction (improvement) in NT-proBNP and an improvement in functional capacity, as measured by 10-meter walk test assessment of gait speed, relative to the placebo group.

Overall, patisiran had an acceptable safety profile, based on an in-depth analysis of cardiac events in both the overall (modified intent-to-treat) population and the cardiac subpopulation. Importantly, in a post hoc analysis of safety data in the modified intent-to-treat population, rates

of any hospitalization and/or all-cause death were 71.8 and 34.7 per 100 patient-years in the placebo and patisiran groups respectively, while the rates of cardiac hospitalizations and/or all-cause death were 18.7 and 10.1 per 100 patient-years in the placebo and patisiran groups respectively. This approximates a reduction in event rate of approximately 50% for all-cause hospitalization and mortality and approximately 45% for cardiac hospitalization and all-cause mortality for patients in the patisiran group compared to those in the placebo group.[\[Solomon 2018\]](#) Similar reductions in the event rates were observed in the cardiac subpopulation in APOLLO (approximately 55% for all-cause hospitalization and mortality and approximately 45% for cardiac hospitalization and all-cause mortality; data on file).

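### The two-week wait after hospitalization does not fit the eight-day Month 12 visit, and the only extension is written for COVID-19, so some late-discharged patients have no stated route to a compliant primary-endpoint walk

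*Protocol*

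**What the plan says.** Four provisions of the current protocol (amendment 3) meet here.

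- **The wait.** Section 6.2.1: "Patients who are hospitalized during the study should wait at least 2 weeks after hospitalization before completing a 6-MWT assessment". It continues: "less time post-hospitalization may be permitted if, in the opinion of the Investigator, the patient is unencumbered due to the recent hospitalization".
- **Acute illness.** If the patient is unwell from an external cause on the test day, "the test should not be done and should be rescheduled for another day within the permitted visit window". Interrupted or unusable tests are likewise to be repeated inside the visit window.
- **The visit and its extension.** Section 6.2 covers the case where a "Month 12 (Day 365-372) study visit is unable to be completed at the study center due to the COVID-19 pandemic impacting activities" at the center, or the patient's access or dosing. After the Medical Monitor is consulted, assessments may then be extended: "Month 12, up to Day 417, but prior to the first dose of open-label patisiran". The same paragraph lets blinded drug continue until the Month 12 assessment. The synopsis, section 3.1, section 4.3.1 and Table 1 footnotes a and b carry the same COVID-19 condition. The limits for Months 6 and 9 are Day 214 and Day 319.
- **The grouping rule.** Section 6.2.1: "A 1.5-month window will be used to group 6-MWT assessments to the Month 6 (Weeks 25-26", and likewise for Months 9 and 12. One walk is allowed per period, and the Month 12 period is Day 320-417. No COVID-19 condition is attached.

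For Years 3 and 4 (section 6.2, Tables 3 and 4) visits may be extended whenever they cannot be completed at the center, with no COVID-19 condition. The first open-label dose is at Week 54 (section 5.2.3.2; Day 379±3 in Table 2), and a delayed dose is allowed up to 7 days after the scheduled visit.

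**The concern.** A wait of at least 14 days cannot fit inside an eight-day visit when discharge comes shortly before or during it. Hospitalization is foreseeable in this population, yet the double-blind extension does not mention it. Open-label visits in Years 3 and 4 have more scheduling freedom than the visit that carries the primary endpoint.

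The waiver covers only patients judged unencumbered, so those caught are the ones still affected by the admission. Hospitalization is also a component of the secondary endpoints and something the drug is expected to reduce. A Month 12 walk lost for this reason is lost through an outcome that may differ by arm. The primary mixed model can use the patient's Month 6 and Month 9 walks, but it relies on missing at random, which is doubtful just after an admission. Change in 6-MWT is also the third component of the win-ratio secondary endpoint.

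**Working it through.** **The plan's own power figure.** Inputs from section 7.1: difference 29 m, SD 75 m, 150 per arm, two-sided alpha 0.05.

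SE = 75 × √(2/150) = 8.66 m; 29/8.66 = 3.35; power = Φ(3.35 − 1.96) = 91.8%. The stated >90% is reproduced.

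**The window.** The earliest walk under the wait is discharge day + 14.

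| Visit | Visit days | Discharge days in conflict | Earliest walk | Extended limit |
|---|---|---|---|---|
| Month 6 | 176-183 | 170-183 | 184-197 | 214 |
| Month 9 | 260-267 | 254-267 | 268-281 | 319 |
| Month 12 | 365-372 | 359-372 | 373-386 | 417 |

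Each visit has 14 conflicting discharge days, and every resulting walk would fall inside the limit already granted for COVID-19. Patients still in hospital when the visit closes are caught too.

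**Month 12 against Week 54.** The dosing window is Day 376-382 and the latest delayed dose is Day 379 + 7 = Day 386.

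- Discharge on Days 359-364: the wait ends on Day 373-378, before the scheduled Day 379.
- Discharge on Days 365-368: it ends on Day 379-382, within the dosing window.
- Discharge on Days 369-372: it ends on Day 383-386, inside the delayed-dose allowance only.

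**Patients caught at Month 12.** The protocol gives no hospitalization rate for this population. As an assumption, take section 1.3.1.1, where the earlier trial's rates "of any hospitalization and/or all-cause death were 71.8 and 34.7 per 100 patient-years in the placebo and patisiran groups"; the cardiac hospitalization and/or death rates there are 18.7 and 10.1. Number per arm = rate × 14/365.25 × 150.

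- All-cause: placebo 0.718 × 14/365.25 × 150 = 4.1; patisiran 0.347 × 14/365.25 × 150 = 2.0; total 6.1 of 300 (2%).
- Cardiac: placebo 1.1; patisiran 0.6; total 1.7 of 300 (0.6%).

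Length of stay is not counted here. Adding a 10-day stay, 1 − exp(−rate × 24/365) gives 4.6% and 2.3% at the all-cause rates, or about 10 of 300. At the cardiac rates it gives about 3.

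**Consequence if all were lost.** With 2% gone (147 per arm) power is 91.2%. It falls below 90% only at 281 or fewer evaluable patients. If affected patients walk 50 to 150 m worse than the rest (assumption), the shift in the treatment difference is (patisiran fraction − placebo fraction) × deficit:

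- All-cause: (0.0133 − 0.0275) × 50 to 150 = −0.7 to −2.1 m.
- Cardiac: (0.0039 − 0.0072) × 50 to 150 = −0.2 to −0.5 m.

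The sign is against patisiran, because more poor walkers are removed from placebo. This simple calculation gives no credit for earlier walks in the mixed model.

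**The case against.** A reader might infer that patients must wait and that the primary endpoint therefore goes missing in the sickest patients. The documents do not support that. The wait is worded as *should* and can be waived. Nothing says a walk after Day 372 is discarded: the grouping rule would place it at Month 12, and further 6-MWT detail sits in a study manual not at hand. Being encumbered by a recent admission may describe temporary after-effects rather than amyloid severity.

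A reader might also take 10 of 300 as the size. That needs a 10-day stay, all-cause rates from a polyneuropathy population that include deaths (whose walks no extension recovers), no waivers and no late walks.

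The bias is small and works against the drug, so it does not favour a false positive. Missing-data handling and sensitivity analyses are left to the statistical analysis plan. A tighter window at the primary time point is a legitimate choice, so the Years 3-4 wording is a comparison and not a contradiction.

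All of this limits the point without removing it. Grouping a late walk does not authorize a site to perform one, and the illness rule points the site to the permitted visit window. The condition that the walk precede open-label drug, and the permission to continue blinded drug until then, appear only in the COVID-19 text. The grouping rule carries neither.

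**Conclusion.** The scheduling conflict is real and in the current text. A patient discharged on Days 359-372 and not judged unencumbered has no stated route to a compliant Month 12 walk; Months 6 and 9 have the same gap. The documents do not show that these walks will be lost, only that their collection is not provided for.

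The size is small: about 2 to 6 of 300 patients at Month 12, roughly twice as many on placebo. Power stays above 90%, and any shift is about 0.2 to 2.1 m against patisiran, compared with a planned 29 m. The counts rest on borrowed rates from another population that combine hospitalization with death, and the shift rests on an assumed 50-150 m deficit. The reason to act is that this loss would depend on a trial outcome and is cheap to prevent. It does not threaten the trial's conclusion.

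**What to change.** In sections 6.2 and 6.2.1 and Table 1 footnotes a and b, let the existing assessment extension (Day 214, 319 and 417) also cover 6-MWTs delayed by hospitalization or acute illness. Keep its condition that the Month 12 walk precede the first open-label dose. Make the matching change in the synopsis and sections 3.1 and 4.3.1, so that the passages agree. The two-week wait, the waiver and the Day 320-417 grouping stay as they are.

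The extended assessment must also be reconciled with the Week 54 passages (section 5.2.3.2, Table 2). For discharges close to Day 372 the wait ends within or after the first open-label dosing window. How that is resolved is for the sponsor; no dosing rule is proposed here.

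The cost is amendment wording, slightly more spread in test dates inside a window the protocol already groups to each visit, and a possible timing conflict with Week 54 dosing for a few patients.
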